### **7.10.2. Subjects Lost to Follow-up**

A subject will be considered lost to follow-up if he/she repeatedly fails to return for scheduled visits and is unable to be contacted by the study site. The following actions must be taken if a subject fails to return to the clinic for a required study visit:

- The site must attempt to contact the subject, reschedule the missed visit as soon as possible, and counsel the subject on the importance of maintaining the assigned visit schedule and ascertain whether or not the subject wishes to and/or should continue in the study.
- Before a subject is deemed lost to follow-up, the Investigator or designee must make every effort to regain contact with the subject (where possible, 3 telephone calls and, if necessary, a certified letter to the subject's last known mailing address or local equivalent methods). These contact attempts should be documented in the subject's medical record.

Should the subject continue to be unreachable, he/she will be considered lost to follow-up.

## **7.11. Pharmacokinetic Assessments**

During the study, predose plasma samples will be collected from all subjects to explore the PK profile of 731, Peg-IFN $\alpha$ , and ETV after combination treatment with or without Peg-IFN $\alpha$  in subjects with CHB. Additionally, postdose samples will be collected at the timepoints outlined in [Table 1](#). Additional details regarding the collection, processing, storage, and shipment of PK samples is described in the Laboratory Manual. Plasma samples of Peg-IFN $\alpha$  and ETV will be collected and stored for future PK analyses if deemed necessary.

**Table 1: Pharmacokinetic Sample Collection**

Time period	Time relative to study drug administration a	Time relative to study drug administration b
Treatment	Predose c	Day 1, Weeks 4 and 24
	30 min to 2 hours postdose	Weeks 2, 8, 12, and 24
	2 to 4 hours postdose	Day 1
	4 to 6 hours postdose	Weeks 16 and 20
	Collect at same time with other central labs	At Unscheduled and Premature Termination Visits d and predose at the Week 44 visit

- a. If the subject administers study drug at home, a pharmacokinetic sample should be collected during the in clinic visit with documentation of date and time of the dose in the subject's source documents.
- b. Sample collection times are targeted times. Samples collected outside of these targeted times will not be considered protocol deviations. The actual sample collection date/time should be accurately recorded in the source documentation.
- c. The predose sample may be collected up to 2 hours prior to study drug administration.
- d. A pharmacokinetic sample should also be collected if an Unscheduled or Premature Termination Visit is performed.

## 7.12. End of Study Definition

The study will be completed when the last subject completes the 12-week follow-up period, or is considered “lost to follow-up” (Section 7.10.2), whichever is later.

## 7.13. Resistance Monitoring

To assess for viral resistance during the study, serum samples from subjects at each visit will be collected (Section 7). Samples from those subjects with evidence of nonresponse to treatment, such as viral breakthrough (ie,  $\geq 1$   $\log_{10}$  increase in on-treatment HBV DNA from on-treatment nadir) will be selected for HBV gene sequencing, with sequence comparisons to Baseline sequences, as well as comparisons to HBV gene sequences from subjects in other treatment groups and HBV database sequences.

# 8. ADVERSE EVENTS

An AE is any untoward medical occurrence in a study subject administered an investigational product(s) regardless of the causal relationship with treatment.

An AE, therefore, can be any unfavorable and unintended sign (including laboratory finding), symptom, or disease temporally associated with participation in an investigational study, whether or not considered drug related. In addition to new events, any increase in the severity or frequency of a pre-existing condition that occurs after the subject signs the ICF for participation is considered an AE. This includes any side effect, injury, toxicity, or sensitivity reaction.

## 8.1. Documenting Adverse Events

Adverse events will be monitored throughout the entire study. Investigators will ask the subject at each visit if they have experienced any untoward effects since the last study visit. All AEs (for all randomized subjects and excluding screen failures) will be entered in the electronic case report form (eCRF) provided: a description of the event, severity, time of occurrence, duration, any action (eg, treatment and follow-up tests), and the outcome should be provided along with the Investigator's assessment of the relationship to the study treatment.

Adverse events will be recorded from the date informed consent is signed through the end of study (completion of follow-up period or if the subject is lost to follow-up).

## 8.2. Assessment of Intensity

The severity of each AE and laboratory abnormality is to be assessed by the Investigator according to the modified Division of AIDS (DAIDS) Table for Grading the Severity of Adult and Pediatric AEs ([Appendix 3](#)), which grades the severity of clinical AEs and laboratory abnormalities in a 4-category system.

For AEs not included in [Appendix 3](#), the following guidelines will be used to describe severity:

- **Mild (Grade 1):** Mild symptoms causing no or minimal interference with usual social and functional activities with intervention not indicated
- **Moderate (Grade 2):** Moderate symptoms causing greater than minimal interference with usual social and functional activities with intervention indicated
- **Severe (Grade 3):** Severe symptoms causing inability to perform usual social and functional activities with intervention or hospitalization indicated (Of note, the term “severe” does not necessarily equate to “serious”)
- **Life-threatening (Grade 4):** Potentially life-threatening symptoms causing inability to perform basic self-care functions with intervention indicated to prevent permanent impairment, persistent disability, or death

Note that an AE or laboratory abnormality that is life-threatening as it exists constitutes an SAE.

## 8.3. Assessment of Causality

All AEs must have their relationship to study drug (731, ETV, or Peg-IFN $\alpha$ ) assessed by the clinician who examines and evaluates the subject based on temporal relationship and his/her clinical judgment. Each AE must be recorded in the source documentation, whether serious or not serious. For the purposes of this study each event is to be assessed with regard to the following causality categorizations, in the Investigator’s considered judgment:

- **Not related:** An AE with sufficient evidence to accept that there was no causal relationship to administration of study drug (eg, no temporal relationship because the study drug was administered after the onset of the event, an investigation showed that study drug was not administered, another cause was proven).
- **Related:** An AE occurred in a plausible time relationship to administration of study drug and that could not be explained by a concurrent disease or other drugs or events. The response to withdrawal of the drug (dechallenge) was clinically reasonable.

## 8.4. Expectedness

An AE is considered “unexpected” if it is not listed in the IB or is not listed at the specificity or severity that has been observed. The CRO and Sponsor Medical Monitors will be responsible for determining whether an AE is expected or unexpected.

## 8.5. Abnormal Laboratory Test Values

In the event of abnormal laboratory test values, the tests should be repeated immediately. If the Investigator considers the abnormality to be clinically significant, it should be reported as an AE and

followed up until it returns to the normal range and/or an adequate explanation of the abnormality is found.

## **8.6. Dose Modification due to Adverse Events**

The dose of Peg-IFN $\alpha$  may be adjusted due to AEs. Where dose adjustment is required for moderate to severe adverse reactions (clinical and/or laboratory) initial dose reduction to 135  $\mu$ g is generally adequate for patients. In some cases, dose reduction to 90  $\mu$ g or 45  $\mu$ g is necessary. Dose increases to or towards the original dose may be considered when the adverse reaction abates. Details of recommended dose reductions of Peg-IFN $\alpha$  are provided in the package insert for the commercially available product used in this study.

There is no dose modification allowed for 731 or ETV.

## **8.7. Adverse Event Follow-up**

After the initial AE or SAE report, the Investigator will follow-up proactively on each subject and provide further information to the CRO/Sponsor on the subject's condition. During the study, all AEs or SAEs should be followed to resolution unless the event is considered by the Investigator to be unlikely to resolve due to the subject's underlying disease, or the subject is lost to follow-up.

## **8.8. Pregnancy**

### **8.8.1. Female subjects who become pregnant**

Any female subject who becomes pregnant while participating in the study will discontinue the study drug(s) immediately ([Section 7.10](#)).

The Investigator will collect pregnancy information on any female subject who becomes pregnant while participating in this study, including the 12-week follow-up period. The initial information will be recorded on the Pregnancy Reporting form and submitted to the CRO Pharmacovigilance group within 24 hours of learning of a subject's pregnancy. Refer to the Study Operations Manual for contact information for reporting a pregnancy.

The subject will be followed to determine the outcome of the pregnancy. The Investigator will collect follow-up information on the subject and the neonate and the information will be forwarded to the Sponsor. Generally, follow-up will not be required for longer than 6 to 8 weeks beyond the estimated delivery date. Any termination of pregnancy will be reported, regardless of fetal status (presence or absence of anomalies) or indication for the procedure.

While pregnancy itself is not considered to be an AE or SAE, any pregnancy complication or elective termination of a pregnancy for medical reasons will be reported as an AE or SAE. A spontaneous abortion (occurring at <22 weeks gestational age) or still birth (occurring at >22 weeks gestational age) is always considered to be an SAE and will be reported as such.

Any post-study pregnancy related SAE considered reasonably related to the study drug(s) by the Investigator will be reported to the Sponsor. While the Investigator is not obligated to actively seek this information in former study subjects, he or she may learn of an SAE through spontaneous reporting.

### **8.8.2. Male subjects with partners who become pregnant**

The Investigator will conduct due diligence to collect pregnancy information on any male subject's female partner who becomes pregnant while the male subject is participating in this study. This applies only to male subjects who receive at least 1 dose of study drug (731, ETV, or Peg-IFN $\alpha$ ).

After obtaining the necessary signed informed consent from the pregnant female partner directly, the Investigator will record pregnancy information on the Pregnancy Reporting form and submit it to the CRO Pharmacovigilance group within 24 hours of learning of the partner's pregnancy. The female partner will also be followed to determine the outcome of the pregnancy. Information on the status of the mother and child will be forwarded to the Sponsor. Generally, the follow-up will be no longer than 6 to 8 weeks following the estimated delivery date. Any termination of the pregnancy will be reported regardless of fetal status (presence or absence of anomalies) or indication for the procedure. Refer to the Study Operations Manual for contact information for reporting a pregnancy.

## **9. SERIOUS ADVERSE EVENTS**

### **9.1. Definition of Serious Adverse Event**

An SAE is any event that meets any of the following criteria:

- Death
- Life-threatening
- Inpatient hospitalization or prolongation of existing hospitalization
- Persistent or significant disability/incapacity
- Congenital anomaly/birth defect in the offspring of a subject who received 731
- Other: Important medical events that may not result in death, be life-threatening, or require hospitalization, may be considered an SAE when, based upon appropriate medical judgment, they may jeopardize the subject and may require medical or surgical intervention to prevent one of the outcomes listed in this definition. Examples of such events are:
  - Intensive treatment in an emergency room or at home for allergic bronchospasm
  - Blood dyscrasias or convulsions that do not result in inpatient hospitalization
  - Development of drug dependency or drug abuse

### **Definition of Terms**

**Life-threatening:** An AE is life-threatening if the subject was at immediate risk of death from the event as it occurred; ie, it does not include a reaction that if it had occurred in a more serious form might have caused death. For example, drug induced hepatitis that resolved without evidence of hepatic failure would not be considered life-threatening even though drug induced hepatitis can be fatal.

**Hospitalization:** AEs requiring hospitalization should be considered SAEs. Hospitalization for elective surgery or routine clinical procedures that are not the result of AEs (eg, elective surgery for a pre-existing condition that has not worsened) need not be considered AEs or SAEs. If anything untoward is reported during the procedure, that occurrence must be reported as an AE, either "serious" or "non-serious" according to the usual criteria.

In general, hospitalization signifies that the subject has been detained (usually involving at least an overnight stay) at the hospital or emergency ward for observation and/or treatment that would not have been appropriate in the physician's office or outpatient setting. When in doubt as to whether "hospitalization" occurred or was necessary, the AE should be considered serious.

**Disability/incapacitating:** An AE is incapacitating or disabling if the experience results in a substantial and/or permanent disruption of the subject's ability to carry out normal life functions.

## **9.2. Reporting Serious Adverse Events**

All SAEs must be reported within 24 hours of learning about the event using the SAE Report form to the CRO Pharmacovigilance group. Refer to the Study Operations Manual for contact information for reporting SAEs.

The initial report should be promptly followed by detailed, written reports, which will include copies of relevant hospital case reports, autopsy reports, and other documents when requested and applicable. This additional information will be requested, if necessary, by the responsible monitor within 5 days of receipt of the alert report. This is to ensure that the initial reporting of SAEs is made to regulatory authorities within the required time period.

For a follow-up report to the authorities, the monitor may be required to collect further information for a final evaluation of the case. Reporting to the respective country regulatory authorities will be the responsibility of the Sponsor and the CRO.

It will be the responsibility of the individual Investigators to inform any local Independent Ethics Committees (IECs) of SAEs as required. Correspondence with the IEC(s) relating to the reporting of SAEs will be retained in the study file.

Serious adverse events will be recorded from the date informed consent is signed through the end of study (completion of follow-up period or if the subject is lost to follow-up).

## **9.3. Overdose**

An overdose is defined as the accidental or intentional administration of any dose of a product that is considered both excessive and medically important. The Medical Monitor may be contacted for questions concerning potential cases of overdose. An overdose is not in and of itself considered to be an AE unless it results in untoward medical effects. Any AE associated with an overdose or incorrect administration of study drug should be entered in the subject's source documentation and Adverse Event eCRF. If the associated AE fulfills the criteria of an SAE, then the event should be reported to the Sponsor or CRO within 24 hours after the site learns of the event.

## **9.4. Management of ALT Elevations**

All subjects participating in the study will be closely monitored for ALT elevations and/or signs of potential decline in hepatic function. Subjects experiencing ALT elevations  $\geq 2 \times$  Baseline or on-treatment nadir and  $> 2 \times$  ULN during study treatment or during post-treatment follow-up should be closely monitored with regular Unscheduled Visits every 1 to 2 weeks at the discretion of the Investigator. At these visits, the following laboratory tests will be performed: ALT, aspartate aminotransferase (AST), total bilirubin (if total bilirubin is elevated, reflex to direct bilirubin), serum albumin, INR and creatine kinase. The Investigator will determine if other Unscheduled Visit

assessments ([Section 7.8](#)) should be performed. Additionally, the following guidance is provided for management of subjects with ALT elevations:

- ALT elevation without declining hepatic function
  - All subjects with an ALT elevation on treatment, defined as ALT  $>2 \times$  Baseline or on-treatment nadir and  $\geq 10 \times$  ULN, should have the ALT findings confirmed within 3 days of receipt of the original results. All subjects should return for an Unscheduled Visit and complete all Unscheduled Visit procedures ([Section 7.8](#)).
  - If the ALT elevation is confirmed, then an additional Unscheduled Visit will be performed to further evaluate the subject. At this visit, the following tests will be performed: ALT, AST, total bilirubin (if total bilirubin is elevated, reflex to direct bilirubin), serum albumin, INR, creatine kinase, HBV DNA, quantitative HBV serologies (HBeAg [reflex qualitative HBeAg if quantitative HBeAg is less than the lower limit of quantification (LLOQ)] and HBsAg [reflex qualitative HBsAg if quantitative HBsAg is  $<$ LLOQ]), HAV IgM, HCV RNA, HDV RNA, and HEV IgM. The Investigator will determine if other assessments specified in [Section 7.8](#) should be performed.
    - If an intercurrent illness is determined to be causal, subjects with an ALT elevation without declining hepatic function and without contraindications may continue assigned treatment (ie, 731, ETV and Peg-IFN $\alpha$  as applicable) and the intercurrent illness should be treated as deemed medically appropriate by the Investigator.
    - In the absence of an intercurrent illness that is determined to be causal, subjects with an ALT elevation without declining hepatic function and without contraindications may continue assigned treatment (ie, 731, ETV and Peg-IFN $\alpha$  as applicable) under close observation.
  - If ALT is rising at the confirmatory visit, subjects should return for an Unscheduled Visit ([Section 7.8](#)) every 2 to 5 days until the ALT elevation has stabilized. At these visits only the following laboratory tests will be performed: ALT, AST, total bilirubin (if total bilirubin is elevated, reflex to direct bilirubin), serum albumin, INR, creatine kinase, HBV DNA, and quantitative HBV serologies (HBeAg [reflex qualitative HBeAg if quantitative HBeAg is  $<$ LLOQ] and HBsAg [reflex qualitative HBsAg if quantitative HBsAg is  $<$ LLOQ]). The Investigator will determine if other assessments specified in [Section 7.8](#) should be performed. Subjects whose ALT has stabilized should continue to be monitored weekly (or more frequently, as deemed necessary by the treating physician) until ALT values return to normal or Baseline levels.
    - Subjects with an ALT elevation without declining hepatic function and without contraindications may continue on 731 and ETV as applicable and have the dose of Peg-IFN $\alpha$  adjusted, if applicable ([Section 8.6](#)). There are no dose adjustments for 731 or ETV.
    - Subjects with an ALT elevation without declining hepatic function and without contraindications should discontinue Peg-IFN $\alpha$  (if applicable) and 731 (if applicable) if the ALT remains persistently  $>2 \times$  ULN elevated for

>8 weeks and there is no decline in viral parameters. Entecavir may be continued at the discretion of the Investigator in accordance with local practice. For information specific to dose modification or interruption, see [Section 7.10.1 “Discontinuation from Treatment.”](#)

- Subjects with an ALT elevation  $>10 \times \text{ULN}$  should consider dose interruption of Peg-IFN $\alpha$  (if applicable). After 8 weeks of interruption, if ALT has not returned to  $<2 \times \text{ULN}$ , subject should discontinue Peg-IFN $\alpha$  (if applicable) and 731 (if applicable). If ALT returns to  $<2 \times \text{ULN}$ , re-introduction of Peg-IFN $\alpha$  (if applicable) should be considered at the Investigator’s discretion. Entecavir may be continued at the discretion of the Investigator in accordance with local practice.
- ALT elevation with declining hepatic function
  - Subjects with confirmed ALT elevation with evidence of declining hepatic function should discontinue Peg-IFN $\alpha$  (if applicable) and 731 (if applicable). Entecavir may be continued at the discretion of the Investigator in accordance with local practice. Elevation of ALT with declining hepatic function is defined as:
    - ALT elevation  $\geq 2 \times \text{Baseline}$  or nadir and  $>2 \times \text{ULN}$  AND
      - Direct bilirubin increase to  $\geq 2 \times \text{Baseline}$  and  $\geq 2 \times \text{ULN}$  OR
      - Albumin decline  $\geq 0.5 \text{ g/dL}$  OR INR  $>2 \times \text{Baseline}$  OR
      - Symptoms of liver inflammation (eg, fatigue, weakness, lack of appetite, nausea, vomiting, jaundice, or discolored feces)
  - Subjects with evidence of declining hepatic function should return for an Unscheduled Visit ([Section 7.8](#)) every 2 to 5 days until the relevant laboratory values stabilize. Subjects whose hepatic function has stabilized should continue to be monitored weekly (or more frequently as deemed necessary by the Investigator) until the relevant laboratory values return to normal or Baseline.

All subjects with ALT elevation without or with declining hepatic function should continue to be followed on their regular study visit schedule, with the addition of Unscheduled Visits ([Section 7.8](#)) as described previously. If the ALT elevation has not substantially resolved by the last study follow-up visit, subjects should continue to return to clinic as deemed medically appropriate by the Investigator and in consultation with the Sponsor. The Unscheduled Visit module in the case report form should be utilized as needed to gather additional clinical and laboratory data until the ALT elevation is documented to be either resolved or resolving (defined as consistent ALT declines of 10% or more or normalization of ALT) on at least 2 successive visits.

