## 7.8. Unscheduled Visit

An Unscheduled Visit may be performed at any time at the discretion of Investigator in order to further evaluate a subject. The specific assessments to be performed at these visits would be determined by the Investigator according to nature of the subject specific follow-up required, however at a minimum the assessments would include the following:

- Vital signs (temperature, heart rate, respiration rate and blood pressure)
- Symptom-directed physical examination
- Review concomitant medications
- Review AEs
- Laboratory analyses (additional details are provided in the Laboratory Manual):
  - Safety labs: chemistry, hematology, coagulation, urinalysis, urine drug test, urine pregnancy test ([Appendix 2](#))

- Virology: HBV DNA, HBV pgRNA, HBsAg, HBeAg, HBcrAg, sample for HBV sequencing, and HBV nucleic acids ([Appendix 2](#))
- PK samples: samples for 731 and Peg-IFN $\alpha$  (if appropriate), and ETV ([Section 7.11](#))

Assessments performed should be documented in the subject's source documentation. Clinical laboratory assessments should be conducted through the central laboratory. The minimum assessments to be completed when managing ALT elevations at an Unscheduled Visit are noted in [Section 9.4](#).

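### Section 9.4 tests direct bilirubin at interim ALT-elevation visits only when total bilirubin is raised, but the stopping rule's direct-bilirubin limb carries no such condition

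*Combined protocol and SAP*

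**What the plan says.** **The stopping rule.** Section 9.4 defines ALT elevation with declining hepatic function as ALT at least 2 × Baseline or nadir and above 2 × ULN, plus any one of four findings: direct bilirubin, albumin, INR or symptoms of liver inflammation. The direct limb ("Direct bilirubin increase to" at least 2 × Baseline and at least 2 × ULN) does not mention total bilirubin. Meeting the rule means stopping 731 and Peg-IFNα. SAP 7.2.2.2 repeats the definition and tabulates it by arm without symptoms.

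**The interim visits.** Subjects reaching the same ALT threshold "should be closely monitored with regular Unscheduled Visits every 1 to 2 weeks at the discretion of the Investigator", and there "the following laboratory tests will be performed: ALT, aspartate aminotransferase (AST), total bilirubin (if total bilirubin is elevated, reflex to direct bilirubin", with albumin, INR and creatine kinase. The reflex condition is repeated for the extra visit after a confirmed elevation. It appears again for the visits every 2 to 5 days when ALT is still rising: "At these visits only the following laboratory tests will be performed: ALT, AST, total bilirubin (if total bilirubin is elevated, reflex to direct bilirubin". Further tests are left to the Investigator.

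**The supporting text.** Section 7.8 lists "Safety labs: chemistry, hematology, coagulation, urinalysis, urine drug test, urine pregnancy test" for a general unscheduled visit, then sends ALT cases back to Section 9.4: "The minimum assessments to be completed when managing ALT elevations at an Unscheduled Visit are noted in" that section. In Appendix 2, Table 2, the elevated-ALT row names total bilirubin and not direct. The clinical chemistry row names both, but its footnote a makes fractionation conditional on total above ULN.

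**The safeguards.** For ALT above 2 × Baseline or nadir and at least 10 × ULN there is a confirmatory visit: "All subjects should return for an Unscheduled Visit and complete all Unscheduled Visit procedures". Also, "All subjects with ALT elevation without or with declining hepatic function should continue to be followed on their regular study visit schedule".

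**The concern.** A stopping rule works only if its inputs are measured when the decision is made. Here the visits and the rule share one ALT threshold, so these are the visits at which the rule is meant to be applied. At a visit with normal total bilirubin, one of its three laboratory limbs is not required to be measured.

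The protocol elsewhere treats direct bilirubin as a quantity in its own right: exclusion criterion 14 sets a separate direct limit of 1.2 × ULN. Footnote a to Table 2 fits neither that criterion nor the chemistry row it annotates. At stake is a possible delay in stopping 731 and Peg-IFNα in a subject whose direct fraction rises while total stays in range. The same limb is also one of the three left in the SAP's by-arm table.

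**Working it through.** The plan states no figure to reproduce. The check has three parts.

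**1. Where direct bilirubin is required, set against where the rule applies**

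| Visit | ALT range | Direct bilirubin |
|---|---|---|
| Every 1 to 2 weeks (9.4) | >2 × ULN | reflex only |
| Confirmatory (9.4 with 7.8) | ≥10 × ULN | full chemistry |
| Extra visit after confirmation (9.4) | ≥10 × ULN | reflex only |
| Every 2 to 5 days, rising ALT (9.4) | ≥10 × ULN | reflex only |
| Scheduled visits (Appendix 1) | any | full chemistry |

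Each Section 9.4 visit also requires the relative rise from Baseline or nadir. The rule starts above 2 × ULN and mandatory full chemistry starts at 10 × ULN, so ALT >2 to <10 × ULN has no confirmatory visit with the full panel. From 10 × ULN upward, only the later follow-up visits are affected.

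**2. How long the limb can go unmeasured**

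This assumes that full chemistry includes direct bilirubin, as the Table 2 row says. From Week 4 the scheduled chemistry visits are nominally 28 days apart (Week 6 has none). The number of interim visits strictly inside 28 days, at one every k days, is floor(27/k):

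- k = 14: 1 visit
- k = 7: 3 visits
- k = 5: 5 visits
- k = 2: 13 visits

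The last two are upper limits, because the 2-to-5-day schedule ends once ALT stabilises. If footnote a were read literally, scheduled chemistry would not close the gap either.

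**3. When a trigger could actually be missed**

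Take *elevated* to mean total above ULN, as in footnote a. Let r = direct ULN / total ULN. Neither ULN is in the documents, so r is an assumption. Direct is a fraction of total, and with no reflex total ≤ULN. The limb needs direct ≥2 × direct ULN = 2r × total ULN. Both can hold only if 2r ≤1, that is r ≤0.5. With total at t × ULN, the direct share of total must be at least 2r/t:

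| r | share needed, t = 1.0 | share needed, t = 0.8 |
|---|---|---|
| 0.20 | 40% | 50% |
| 0.25 | 50% | 62.5% |
| 0.30 | 60% | 75% |
| 0.40 | 80% | 100% |
| 0.50 | 100% | impossible |
| 0.60 | impossible | impossible |

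The condition of at least 2 × Baseline must hold as well. With baseline direct b in ULN units, the limb's threshold is max(2, 2b) × ULN, so a baseline above ULN makes a hidden trigger rarer still (b = 1.2 gives 2.4 × ULN). A miss therefore needs both a low ULN ratio and a total made up largely of direct bilirubin. It also needs albumin, INR and symptoms all to be silent.

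**The case against.** Reflex testing can be defended. A normal total already bounds the direct fraction, and for r above 0.5 it rules out the limb altogether. Albumin and INR are measured unconditionally at these visits, symptoms including jaundice also trigger stopping, and the Investigator may add any Section 7.8 test. From 10 × ULN the full panel is required once, scheduled chemistry continues throughout, and the Laboratory Manual, which is not available here, may have direct run with total anyway. The study was terminated in July 2022, so no protocol edit can help its subjects. All of this stands, and it limits the size of the point. It does not remove the mismatch: the protocol makes a stopping-rule input optional at the visits where the rule is applied.

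Two stronger readings are tempting.

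- **That the SAP needs a rule for missing baseline direct bilirubin.** The documents do not support this. Exclusion 14 requires a Screening direct value, Section 7.1 grants no waivers, and SAP 3.6.4 and 3.6.5 take the last nonmissing value on or before first dose. SAP 3.4 also provides for direct values below 0.1 mg/dL, which fits routine reporting. Only footnote a, read literally, points the other way, and that reading would make exclusion 14 untestable in anyone with a normal total.
- **That the SAP leaves the count undefined when direct is unmeasured.** SAP 3.5.1 does not impute, and SAP 7.2.2.2 counts criteria met at the same visit, so an unmeasured limb is simply not counted. The denominator wording does not name the component, but that is a matter of detail.

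**Conclusion.** The mismatch between the Section 9.4 testing schedule and its own stopping rule is real on the text, and it is worth a cheap correction if the protocol is reused. With total ≤ULN, the direct limb can go unmeasured between scheduled chemistry visits, nominally up to 28 days, for ALT >2 to <10 × ULN. At higher ALT it can go unmeasured at the follow-up visits after the confirmatory one.

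The number of subjects affected cannot be derived from the documents and may be zero. The point has consequences only if the direct ULN is at most half the total ULN, and even then few misses are expected. The 28-day bound assumes that routine chemistry reports direct bilirubin.

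A reader might infer that the stopping rule fails to protect subjects or that the safety table is unreliable. Neither follows: the other limbs remain active, the table is descriptive, and SAP 7.2.2.2 lists every subject who meets at least one criterion.

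**What to change.** For any reuse of the protocol text:

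- delete the reflex condition wherever it appears in Section 9.4, and delete footnote a to Table 2;
- add direct bilirubin to the elevated-ALT row of Table 2;
- report direct with total at every Section 9.4 visit.

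The cost is one extra analyte on serum already drawn, plus matching wording in Appendix 2, Section 9.4 and the Laboratory Manual.

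For this study's report nothing is essential, and no missing-baseline rule should be added. At most, the SAP 7.2.2.2 table could carry a footnote giving, by arm, the number of subjects who met the ALT limb at a visit with no direct bilirubin value. A count of subjects with no post-baseline direct value at all would not serve, because someone untested at an interim visit may well have values from scheduled visits. If the SAP is already final, its Section 1 allows the footnote to be documented in the Synoptic CSR. The cost is one line.
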